8.4 Detection of Bias

Lack of protocol compliance and the potential for biased statistical analyses will be examined by assessing the incidence of important protocol deviations in each cohort. The clinical study team will identify and document the criteria for important protocol deviations.

8.5 Outliers

Outlier data will not be excluded unless scientifically justified.

PK plasma concentration data will be evaluated for outliers by visual inspection and decisions to re-assay individual samples will be made in accordance with standard PKDM practices.

8.6 Distributional Characteristics

The investigation of distributional characteristics for the proposed summaries of the data is not needed for this study.

8.7 Validation of Statistical Analyses

Programs will be developed and maintained, and output will be verified in accordance with current risk-based quality control procedures.

Tables, figures, and listings will be produced with validated standard macro programs where standard macros can produce the specified outputs.

The production environment for statistical analyses consists of Amgen-supported versions of statistical analysis software SAS version 9.3. or later

9. Statistical Methods of Analysis

9.1 General Considerations

In general, the data will be presented in the CSR by considering RRMM patient groups (Cohort 1, Cohort 2 and Arm 2) and NDMM patient groups (Arm 1, Cohort 4 and Arm 3) separately. The data will be presented by each assigned dose cohort and by combined dose cohort in RRMM group and NDMM group. The dose cohort grouping is as follows.

RRMM patient groups:

1. RRMM 56 mg/m² (n=10) – Cohort 1
2. RRMM 70 mg/m² (n=12) – Cohort 2
3. RRMM 70 mg/m² (n=34) – Arm 2
4. RRMM 70 mg/m² (n = 46) – Cohort 2 + Arm 2

NDMM patient groups:

1. NDMM 70 mg/m² (n=9) – Arm 1
2. NDMM 56/70 mg/m² (n=9) – Cohort 4 (step up dosing)
3. NDMM 70 mg/m² (n=18) – Arm 1 + Cohort 4
4. NDMM 56 mg/m² (n=33) – Arm 3

Summary statistics will be provided for selected study variables. For continuous variables, the number of subjects with non-missing data (n), mean, standard deviation, median, minimum, and maximum will be presented. For discrete variables, the frequency and percentage distribution will be presented. Unless otherwise stated, the denominator for percentages is the number of subjects in the analysis set of interest for the summary. Graphical methods will be used, as appropriate, to illustrate study endpoints.

Confidence interval, when presented, will be constructed at the 95% level. For binomial variable, exact distribution methods will be employed. The distribution of time-to-event endpoints will be summarized by Kaplan-Meier method. Quartiles including median will be estimated by Kaplan-Meier along with their 95% confidence intervals.

Individual subject data recorded on the electronic case report forms (eCRFs) and any derived data will be presented in dataset tabulations.

9.2 Subject Accountability

The following subject disposition information will be summarized as follows

- Number of **enrolled** subjects
- Number of subjects in Safety Analysis Set
- Number (%) of subjects in Response Evaluable Analysis Set
- Number (%) of subjects who discontinued treatment
- Number (%) of subjects who discontinued the study
- Primary reason for study discontinuation
- Primary reason for carfilzomib discontinuation

In addition, the number (%) of subjects who had done the following on-study procedures will be reported: stem cell collection, autologous stem cell transplant, allogeneic stem cell transplant.

The percentages are based on the number of subjects in the Safety Analysis Set.

9.3 Important Protocol Deviations

Important Protocol Deviations (IPDs) categories are defined by the study team before the first subject's initial visit and updated during the IPD reviews throughout the study prior to database lock. These definitions of IPD categories, subcategory codes, and descriptions will be used during the course of the study. Eligibility deviations are defined in the protocol. All IPDs will be summarized by category and sub-category for the Safety analysis set.

9.4 Demographic and Baseline Characteristics

9.4.1 Demographics and Baseline Characteristics

The following demographic and baseline characteristics will be summarized for the Safety analysis Set:

- Age (years) and age categorized (years) as: < 65, 65 - < 75, and \geq 75;
- Sex (Male, Female);
- Ethnicity (Hispanic or Latino, Non-Hispanic or Latino)
- Race (White and other categories depending on frequency observed)
- ECOG performance status (0, 1, 2)
- Weight (kg)
- Height (cm)
- Body surface area (m^2)

9.4.2 Medical History

The number (%) of subjects who experienced a prior disease or disorder will be summarized by system organ class and preferred term for the Safety Analysis Set.

9.4.3 Disease Characteristics

The following disease characteristics will be summarized for the Safety Analysis Set:

- Time (months) since initial diagnosis, defined as date of informed consent signed minus date of diagnosis
- Type of measurable disease (SPEP and UPEP, SPEP, UPEP, SFLC only)
- Heavy chain and light chain status
- Plasma cell involvement (%) as assessed with bone marrow assessment (< 50%, \geq 50%, unknown or missing)
- **Cytogenetic** risk group determined by central laboratory FISH (standard risk, high risk, unknown).
- **Cytogenetic risk group determined by local laboratory FISH (standard risk, high risk, unknown)**
- Baseline beta2 microglobulin (mg/L) (< 3.5, 3.5 - < 5.5, \geq 5.5 mg/L)
- Baseline albumin (g/dL) (as continuous variable; <3.5, \geq 3.5 g/dL)
- International Staging System (ISS) stage at diagnosis (I, II, III, unknown)
- ISS stage at baseline (I, II, III, **unknown**)
- Revised ISS at baseline (I, II, III, **unknown**): **FISH data from central laboratory**
- **Revised ISS at baseline (I, II, III, unknown): FISH data from local laboratory**

9.4.4 Prior Cancer Therapies

The following information related to prior cancer therapy will be summarized for the RRMM subjects in the Safety analysis set:

- Number (%) of subjects with at least one systemic anti-myeloma therapy, transplant, radiation or multiple myeloma-related surgery, respectively.
- Number of regimens of prior treatment (1, 2, etc.) for multiple myeloma
- Best response to most recent prior regimen
- Refractory status to any prior regimen and to most recent prior regimen (bortezomib, lenalidomide, bortezomib and lenalidomide)

9.5 Efficacy Analyses

The primary analysis of efficacy will be based on the Safety Analysis Set. Additionally, the response data (ORR, CRR) may also be analyzed based on the Response-evaluable Analysis Set.

9.5.1 Overall Response Rate and Complete Response Rate

The number (%) of subjects with a best response of sCR, CR, VGPR, PR, SD, PD or NE will be summarized.

Overall response rate is defined as the proportion of subjects for whom the best overall confirmed response is sCR, CR, VGPR, or PR as determined by International Myeloma Working Group Uniform Response Criteria (IMWG-URC) per investigator. The ORR along with the associated 95% exact binomial confidence interval (Clopper-Pearson method) will be determined.

The Complete Response rate (CRR), defined as the proportion of subjects with the best overall confirmed response of complete response (CR) or better, will be determined along with the 95% exact binomial confidence interval.

Same summary and analysis for ORR will be repeated based on ORCA assessments.

9.5.2 Progression-Free Survival

Progression free survival (PFS) is defined as number of months (one month = 30.4 days) between start of treatment and first evidence of documented disease progression or death (due to any cause), whichever occurs first. Disease progression will be determined using IMWG-URC and will be determined by the investigator.

- $PFS = (Earliest\ date\ of\ disease\ progression,\ death,\ or\ censoring\ -\ Date\ of\ first\ dose\ +\ 1) / 30.4$

Progression-free survival will be right-censored for subjects who met one of the following conditions: 1) no baseline disease assessments, 2) non-protocol systemic anticancer treatment started before documentation of PD or death, 3) death or disease progression after more than 1 missed disease assessment visit, or 4) alive and does not have documentation of PD before a data analysis cutoff date. These conventions are based on the May 2007 FDA Guidance for Industry, 'Clinical Trial Endpoints for the Approval of Cancer Drugs and Biologics' (www.fda.gov/cder/guidance/7478fnl.htm). For such subjects, the primary analysis of PFS will be right-censored according to the conventions described in [Table 4](#).

The Kaplan-Meier curves will be used to estimate the distribution of PFS and the median and other quartiles in addition to the corresponding two-sided 95% confidence intervals.

Duration of follow-up for PFS will be summarized according to the Kaplan-Meier estimate of potential follow-up also termed "reverse Kaplan-Meier" ([Schemper 1996](#)).

Same summary and analysis for PFS will be repeated based on ORCA assessments.

Table 4. Conventions for Censoring for PFS

Situation	Date of Progression or Censoring	Outcome
No baseline disease assessments	Date of first dose	Censored
New anticancer therapy started before documentation of PD or death	Date of last disease assessment prior to start of new anticancer therapy	Censored
Death or PD immediately after more than 1 consecutively missed disease assessment visit	Date of last disease assessment visit before the first missed visit	Censored
Alive and without PD documentation	Date of last disease assessment	Censored
Lost to follow up or withdrawn consent	Date of last disease assessment	Censored
Death or PD between planned disease assessments	Date of death or first disease assessment showing PD, whichever occurs first	Progressed
Death before first disease assessment	Date of death	Progressed

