10.1.5 MYELOMA RESPONSE ASSESSMENT

Response will be determined by the investigator based on the disease assessments described above and the IMWG-URC (see definitions in [Appendix C](#)). Myeloma response laboratory studies will be drawn at the beginning of each cycle before treatment. The following confirmatory assessments are required for all response categories (stringent complete response [sCR], CR, VGPR, and PR) and progressive disease:

- All laboratory-based progressive disease and all responses require 2 consecutive assessments made at any time before initiation of any new (ie, off protocol) therapy. Confirmatory lab samples should be separated by at least 1 calendar day
- Progressive disease by nonlaboratory-based assessment (ie, plasmacytoma or skeletal lesion) does not require confirmatory report
- All response categories also require no evidence of progression including new bone lesions, if radiographic studies are performed
- Confirmation of CR or sCR requires local pathology review of a bone marrow biopsy or aspirate (a repeat confirmatory bone marrow sample is not required)
- Extramedullary plasmacytoma evaluation is required to confirm PR, CR, or sCR (if present at baseline; [Rajkumar, 2011](#))

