13.6 HANDLING OF MISSING DATA

Missing data for partial dates for AEs or concomitant medication may be imputed according to prespecified, conservative imputation rules. Details of missing data handling and imputation rules will be specified in the statistical analysis plan.

Subjects with no postbaseline response assessments will be classified as nonresponders in the estimation of ORR and CRR.

Progression and survival data will be collected for all subjects on study. For subjects who discontinue without having experienced progression or death, progression will be censored at the time of the last on-study disease assessment demonstrating lack of progression. Details of censoring rules will be specified in the statistical analysis plan.

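### SAP Table 4 censors a single unconfirmed laboratory progression followed by new therapy at the visit that showed it; protocol 13.6 censors one visit earlier, and the confirmation rule for PFS and DOR is only implied

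*SAP*

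**What the plan says.** **Event.** SAP 9.5.2 ends PFS at the "first evidence of documented disease progression or death (due to any cause), whichever occurs first". The next sentence reads: "Disease progression will be determined using IMWG-URC and will be determined by the investigator". Table 4 dates the event as "Date of death or first disease assessment showing PD, whichever occurs first".

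**Confirmation.** Protocol 10.1.5 states: "All laboratory-based progressive disease and all responses require 2 consecutive assessments made at any time before initiation of any new (ie, off protocol) therapy". It lets the samples be as little as one calendar day apart and exempts progression found by imaging or as a skeletal lesion or plasmacytoma. Protocol Appendix C, the study's summary of IMWG-URC, also requires two consecutive assessments for progression on study. SAP 5 repeats the 10.1.5 rule, but under the definition of best overall response by investigator.

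**Censoring in the SAP.** One Table 4 row covers "New anticancer therapy started before documentation of PD or death" and gives the censoring date as "Date of last disease assessment prior to start of new anticancer therapy". The rows for subjects alive without documented progression, and for those lost or withdrawn, use the last disease assessment with no further condition. SAP 9.5.3 takes the progression and censoring dates for DOR from the PFS rules.

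**Censoring in the protocol.** For subjects who discontinue without progression or death, protocol 13.6 censors at "the last on-study disease assessment demonstrating lack of progression" and leaves the details to the SAP. SAP 10 declares no departures from the protocol's analyses.

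**The concern.** Three things are left open or inconsistent.

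1. SAP 9.5.2 and Table 4 never use the word confirmed for progression and never define what counts as documenting it. SAP 9.5.1 does use the word for response. A programmer could take the first progression recorded by the investigator as the event.
2. On the confirmed reading, one laboratory progression followed by new therapy without a repeat sample is not an event. Table 4 then censors at the last assessment before the new therapy, which is the visit that showed progression. The subject is credited with progression-free time up to a visit that did not show freedom from progression. Protocol 13.6 would not do that.
3. These subjects are censored because a progression signal led to a change of therapy. Kaplan-Meier estimation assumes that censored subjects carry the same later risk as those still followed, and here they plainly do not. The direction is towards longer PFS and DOR. No stated sensitivity analysis shows by how much.

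**Working it through.** The plan gives no PFS or DOR assumption, so there is no figure of its own to reproduce. The check is textual, followed by an illustration.

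**Step 1. Is unconfirmed progression an event?** Set side by side, SAP 9.5.2 sends the determination of progression to IMWG-URC. Protocol Appendix C and 10.1.5 and SAP 5 all require two consecutive assessments for laboratory progression. No passage says that a single laboratory value is enough. The phrases about first evidence and first assessment showing progression then fix the date, namely the first of the two assessments. SAP 9.5.3 handles response in the same way, dating it from the first observation before confirmation. The passages can be reconciled, but only by inference.

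**Step 2. What happens to one illustrative subject?** Assumed: first dose on day 0, laboratory progression first seen at Cycle 7 Day 1 (6 × 28 = day 168), new therapy a week later, no second sample. The previous assessment was Cycle 6 Day 1 (5 × 28 = day 140). SAP formula: PFS = (date − first dose + 1)/30.4.

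| Rule | Status | Time (months) |
|---|---|---|
| Single progression counted | Event | (168 + 1)/30.4 = 5.56 |
| Confirmation required, Table 4 date | Censored | (168 + 1)/30.4 = 5.56 |
| Confirmation required, protocol 13.6 date | Censored | (140 + 1)/30.4 = 4.64 |

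The first two rows differ only in status. The last two differ by 28/30.4 = 0.92 months. In Active Follow-up, with visits every 56 days, the gap is 56/30.4 = 1.84 months.

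**Step 3. Effect on the median.** Let g be the share of events that turn into censored observations at the same time. For exponential PFS the hazard estimate is events divided by person-time, so it falls by the factor (1 − g) and the median rises by 1/(1 − g):

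- g = 5%: 1/0.95 = 1.05
- g = 10%: 1/0.90 = 1.11
- g = 20%: 1/0.80 = 1.25

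The same factors apply to DOR, with g taken among events in responders.

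**Step 4. How much of this is the date, and how much the status?** Assume a 20-month median (not in the documents) and g = 10%. Person-time per event is 20/ln 2 = 28.85 months.

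- Table 4 date: 20/0.90 = 22.22 months.
- Protocol 13.6 date, 28-day spacing: ln 2 × (28.85 − 0.10 × 0.92)/0.90 = 22.15 months.
- Protocol 13.6 date, 56-day spacing: ln 2 × (28.85 − 0.10 × 1.84)/0.90 = 22.08 months.

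Correcting the date restores agreement with the protocol but removes little of the shift. Nearly all of it comes from the change of status, which only a sensitivity analysis can show.

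**The case against.** A reader might infer that the documents hold two conflicting rules, with a single laboratory progression an event under SAP 9.5.2 and censored under the protocol. They do not support that. The sentence after the PFS definition brings in IMWG-URC, and with it the two-assessment requirement. What is missing is an explicit statement, and that gap stands.

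A reader might also infer that confirmation is possible only at the End of Treatment draw, since subjects with progression stop treatment and do not enter Active Follow-up. That is too strong. A repeat sample may be taken one calendar day later, and a single laboratory value is not yet progression, so a subject who continues is assessed again on Day 1 of the next cycle. Still, no passage schedules a prompt repeat sample, so missed confirmation is possible. How often it would occur is unknown.

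Other objections limit the point without removing it:

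- Protocol 13.6 delegates censoring details to the SAP. That allows the SAP to add rules. It does not explain why the SAP drops the protocol's condition while declaring no changes.
- For most censored subjects the last assessment shows no progression, so both wordings give the same date. The difference is confined to laboratory-only progression without a repeat sample.
- PFS is repeated with the computational assessment (ORCA). Its algorithm is in a separate document, so whether it covers this case cannot be judged here.
- PFS and DOR are secondary, and SAP 2.2 plans no formal testing.

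**Conclusion.** The point holds in a narrow form. The confirmed reading is the better one, but SAP 9.5.2 and Table 4 leave it implicit. On that reading, Table 4 censors an unconfirmed laboratory progression followed by new therapy at the visit that showed it, which departs from protocol 13.6 by one visit (0.92 months on treatment, 1.84 in Active Follow-up). The censoring is linked to progression and pushes PFS and DOR upwards.

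The factors of 1.05, 1.11 and 1.25 rest on an exponential distribution and assumed shares of 5%, 10% and 20%. They show a range and do not predict the result. Deaths and progressions found other than by laboratory values cannot be affected, so g can be no larger than the laboratory-only fraction of events.

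It may be tempting to conclude that a single unconfirmed laboratory progression should be the primary event. The documents do not support that: it would contradict protocol 10.1.5, Appendix C and SAP 5.

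**What to change.** 1. In SAP 9.5.2 and 9.5.3, state that laboratory progression must be confirmed as in SAP 5 and is dated at the first of the two consecutive assessments. Define documentation of progression in the same terms. Keep confirmed progression as the primary rule.
2. In Table 4, in the rows for new therapy, alive without documented progression, and lost or withdrawn, replace the last disease assessment with "the last on-study disease assessment demonstrating lack of progression", as in protocol 13.6. In the new-therapy row, keep the condition that this assessment precedes the new therapy.
3. Add one sensitivity analysis of PFS and DOR in which a single unconfirmed laboratory progression, followed by new therapy, withdrawal or end of follow-up, is an event at that assessment.

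The cost is a few lines of SAP wording and one extra run. The sensitivity analysis may show somewhat shorter PFS and DOR than the primary analysis.

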9.5.3 Duration of Response

Duration of response (DOR) will be calculated for subjects who achieve a PR or better. For such subjects, the duration of overall response is defined as the time (months) from first documentation of response to disease progression or death due to any cause. Dates of progression and censoring will be determined as described for the analysis of PFS.

$$DOR = (Earliest\ date\ of\ disease\ progression,\ death,\ or\ censoring\ -\ Date\ of\ first\ observation\ of\ PR\ or\ better\ before\ confirmation\ +\ 1) / 30.4$$

Kaplan-Meier methods will be used to estimate the distribution of DOR and the median and other quartiles in addition to the corresponding two-sided 95% confidence intervals; a figure showing the estimated DOR distribution will be provided.

9.6 Safety Analyses

All safety analyses will be based on the Safety Analysis Set.

9.6.1 Adverse Events and Disease-related Events

The Medical Dictionary for Regulatory Activities (MedDRA) version 21.0 or later will be used to code all adverse events (AEs) to a system organ class (SOC) and a preferred term (PT). The severity of AEs will be coded according to NCI-CTCAE v 4.03.

Treatment emergent adverse events will be summarized based on the number (%) of subjects experiencing events by MedDRA SOC and PT. The denominator for the percentage will be based on the number of subjects in the Safety Analysis Set.

Summaries of the subject incidence of the following TEAEs will be provided by SOC and/ or PT:

- All TEAEs
- TEAEs grade 3 or higher
- Fatal TEAEs
- Serious TEAEs
- TEAEs leading to withdrawal of carfilzomib
- Treatment-related TEAEs
- Treatment-related TEAEs grade 3 or higher
- **Treatment-related fatal TEAEs**
- **Treatment-related serious TEAEs**
- **Treatment-related TEAEs leading to withdrawal of carfilzomib**

Summaries that are displayed by SOC and PTs will be ordered by descending order of incidence of SOC and PT within each SOC for the total group. Summaries of TEAEs, and SAEs will be tabulated by SOC, PT and grade. Summaries of TEAEs, treatment-related AEs, and SAEs will also be provided by descending order of incidence of PTs in the total group

All TEAEs will be included in listings by subject. Listings of AEs determined to be DLTs, SAEs, AEs leading to discontinuation of study and AEs leading to discontinuation of investigational product will be provided.

A summary of the number of deaths and the cause of death, classified by deaths within 30 days of last dose of study drug and deaths more than 30 days after the last dose, will be provided.

Subject incidence of adverse events of interest (standardized MedDRA queries (**SMQ**) and/or Amgen MedDRA queries (**AMQ**)) will also be summarized according to their categories, PTs and grade. The adverse events of interest would include

- Acute renal failure (SMQ Narrow search)
- Cardiac arrhythmias (SMQ Narrow search)
- Cardiac failure (SMQ Narrow search)
- **Cardiomyopathy (SMQ Narrow search)**

- Dyspnoeas (HLT) - MedDRA Search Strategy HLT
- Embolic and thrombotic events, venous (SMQ Narrow search)
- Haematopoietic erythropenia (SMQ Broad search)
- Haematopoietic leukopenia (SMQ Narrow search)
- Haematopoietic thrombocytopenia (SMQ Narrow search)
- Haemorrhage terms (excl laboratory terms) (SMQ Narrow search)
- Hepatic failure, fibrosis and cirrhosis and other liver damage-related conditions (SMQ Narrow search)
- **Hepatitis B virus reactivation (AMQ including PTs: Hepatitis viral, Hepatitis acute, Hepatitis B, Acute hepatitis B, Hepatitis B reactivation, Hepatitis B DNA assay positive, Hepatitis B DNA increased)**
- Hypertension (SMQ Narrow search)
- Infusion reactions – (AMQ Narrow search)
 - event on same date of any Carfilzomib dosing
 - event on same date of first Carfilzomib dosing
- Interstitial lung disease (SMQ Narrow search)
- Ischaemic heart disease (SMQ Narrow search)
- Liver related investigations, signs and symptoms (SMQ Narrow search)
- Myocardial infarction (SMQ Narrow search)
- **Peripheral neuropathy (SMQ Narrow search)**
- **Progressive multifocal leukoencephalopathy (AMQ Narrow search)**
- Pulmonary hypertension (SMQ Narrow search)
- Respiratory failure (SMQ Narrow search)
- Respiratory tract infections (HLGT)
- Reversible posterior leukoencephalopathy syndrome (AMQ Narrow search)
- Torsade de pointes/QT prolongation (SMQ Narrow search)
- Tumour lysis syndrome (SMQ Narrow search)

